6.1. Study Design

Patients receiving aRCC treatment (see [Table 4](#)), between April 2018 and the present, who have no prior aRCC treatment in their claims history will be identified for this study. The index date for each analysis will be defined as the date of initiation of the aRCC treatment. Patients must have at least 2 RCC diagnoses at least 30 days apart to be included. Patients must also have 2 secondary malignancy ICD9 or ICD10 codes (often used in claims data to suggest cancer metastases) at least 30 days apart in the 12 months pre and one month post index aRCC treatment. [CCI](#)

Various algorithms and temporal relationships between the secondary malignancy codes, RCC diagnosis codes and other cancer codes were explored toward developing the criteria for metastatic advanced RCC for this study.

Study will require a minimum of 12 months of enrollment prior to the index date. Feasibility was assessed for various lengths of continuous enrollment criteria (3, 6 and 12 months post index date) toward understanding sample sizes available for analysis and follow-up periods. Study outcomes will be assessed for three patient cohorts (3, 6 and 12 month cohorts) according to their available months of continuous enrollment.

PFIZER CONFIDENTIAL

First line therapy cohorts will first be presented for all patients regardless of follow-up time available. Baseline characteristics, costs and utilization will be measured over the 6 months prior to the index date. Duration of therapy and utilization analysis will require at least 6 months of post-index enrollment, with sub-analysis preformed on the cohorts with 3-months and 12-months of post-index enrollment. Utilization and cost will be performed per-utilizer-per-month (PUPM), and then separately for each of the cohorts with 3-month, 6-month and 12-months of post-index enrollment.

The analysis will focus on, but is not limited to, the following regimens:

- a. **Combo IO:** nivolumab combined with ipilimumab;
- b. **Monotherapy TKI:** sunitinib, cabozantinib, and pazopanib;
- c. **Combo TKI + IO:** avelumab in combination with axitinib, pembrolizumab in combination with axitinib;
- d. **Other:** all others regimens.

PFIZER CONFIDENTIAL

[figure not shown]
[figure not shown]
[figure not shown]

Figure 1: Cohort Identification

Analysis 1. Treatment Patterns and Duration

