Treated Period Follow-Up. Patients will be followed over the period treated with advanced RCC therapy. Time treated will be defined as the time from the index date to the date of the end of the last advanced metastatic RCC prescription (end of supply for orals/administration date plus 30 days for injectables), end of enrollment, end of follow up, or death (see more specifics on oral versus injectable rules in [6.3.1 Variables](#) section of this protocol).

Analysis 2. Describe various treated populations of interest by demographics, clinical characteristics, as well as cost and utilization

Describe the demographics and other baseline characteristics of the first-line treated cohorts of interest identified in the treatment patterns analysis (Analysis 1) for RCC patient as follows:

Baseline Characteristics (see [6.3.2 Baseline Characteristics](#)):

- Age at index;
- Gender;
- Race;
- Region;

PFIZER CONFIDENTIAL

- Payor;
- Clinical characteristics: Quan-Charlson Comorbidity Index (CCI) scores and baseline comorbidities;
- Prior treatment (6 months prior) - nephrectomy, radiation/ablation, interferon, high-dose interleukin-2, other anti-neoplastic medications;
- Secondary malignancy locations (6 months prior);
- Baseline costs of care (6 months prior);
- Baseline health care resource utilization (6 months prior).

Analysis 3: Evaluate the key outcomes of interest for advanced RCC therapy regimens toward demonstrating existing unmet needs in RCC given currently available therapies (eg, ipilimumab/nivolumab).

Treatment duration, discontinuation, interruption, switching and therapy augmentation will be presented, as will the burden of disease costs and health care utilization. Survival will also be explored, although regimens are too new for extensive follow-up time.

Overall Outcomes Study Period. For the outcomes analysis, follow-up will be defined as the time from the index date to the end of specified follow up period of 6 months, end of enrollment, or death. Follow-up may vary given sample sizes of study population, with by subanalysis using 1-year or 2-years of follow-up time from study index date for certain sub-populations.

Outcomes include:

- **Time to Treatment Failure (TTF)** – First line time to treatment failure (TTF) is defined as the time from first-line therapy start to treatment discontinuation for any reason, including switched, augmented therapy, end of enrollment, death.

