6.2.1. Inclusion Criteria

Subjects will be selected irrespective of their survival status. Patients must meet all of the following inclusion criteria to be eligible for inclusion in the study:

- **Index date:** The first prescription or administration of one of the medications indicated for advanced RCC recorded in the database between April 2018-March 31, 2019, among those with no aRCC treatment in their history.
- Age 18 years or older in the year of the index first line therapy prescription.
- 2 or more RCC diagnoses (ICD-9: 189.0; ICD-10: C64.1, C64.2, C64.9) at least 30 days apart, in the 1 year prior to the index date until 30 days post index date.

PFIZER CONFIDENTIAL

- 2 or more code for secondary malignancy codes indicating possible diagnoses for metastatic disease at least 30 days apart, in the 1 year prior to the index date until 30 days post index date. (ICD-9: xx-199.xx; ICD-10: C77-C79, except ICD9: 198.0 Secondary malignant neoplasm of the kidney and ICD10: C79.0 Secondary malignant neoplasm of the kidney and renal pelvis).
 - CCI [REDACTED]
- Continuous enrollment from 12 months prior to the index date. Patients will be required to have continuous enrollment from their index date until the end of the available data. This will allow for sub-analysis of cohorts with 3 months, 6 months and 12 months of available data.

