6.3.2. Baseline Variables

Table 6. Baseline Variables

[figure not shown]
Variable	Operational definition
Baseline demographics	
Index Date	Date of first RCC diagnosis on record
Index Year	Index year for the patient
Age	Continuous: Years Patient age at index date
Sex	Categorical: Male or female
Insurance Coverage	Categorical: Commercial, Medicare, or Medicaid
US Region	Categorical: Northeast, Midwest, South, West
Race	Categorical: based on each database
Clinical characteristics	
Time to systemic therapy <1 year	From IMDC: <1 year from time of diagnosis to systemic therapy
NCI Charlson comorbidity index (DCI)	Categorical: 0, 1-2, 3+
History of smoking	Categorical: Yes/No Prior history of smoking – record of smoking cessation medication or V code.
History of systemic therapy	Categorical: Yes/No A record of being given certain systemic drugs (interferon, interleukin 2, gemcitabine and doxorubicin)
History of surgical resection	Categorical: Yes/No History of nephron sparing or radical nephrectomy. ICD-10-CM Z90.5/ICD-9-CM V45.73 Acquired absence of kidney.

PFIZER CONFIDENTIAL

Variable	Operational definition
History of radiation therapy	
Categorical: Yes/No
 
ICD-10-CM Z51.0/ICD-9-CM V58.0 Encounter for radiotherapy.
 
ICD-10-PCS › D › Urinary System:
 
• DT0 Beam Radiation;• DT1 Brachytherapy;• DT2 Stereotactic Radiosurgery;• DTY Other Radiation. 
CPT Codes:
 
77401 Radiation treatment delivery, superficial and/or ortho voltage, per day;
 
77402 Radiation treatment delivery, >1MeV; simple;
 
77407 intermediate;
 
77412 complex.
 
New Codes
 
77085 Dual-energy x-ray absorptiometry (DXA), bone density study, 1 or more sites; axial skeleton (eg, hips, pelvis, spine), including vertebral fracture assessment.
 
77086 Vertebral fracture assessment via dual energy X-ray absorptiometry (DXA).
 
77306 Teletherapy isodose plan; simple (1 or 2 unmodified ports directed to a single area of interest), includes basic dosimetry calculation(s).

PFIZER CONFIDENTIAL

[figure not shown]

Variable	Operational definition

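### Prior treatment and metastatic sites are searched over 6 months, although 12 months of enrollment is required and metastasis eligibility uses a full year

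*Combined protocol and SAP*

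**What the plan says.** Section 6.1 sets a general baseline rule: "Baseline characteristics, costs and utilization will be measured over the 6 months prior to the index date". Its list for Analysis 2 repeats the 6 months for two history items: "Prior treatment (6 months prior) - nephrectomy, radiation/ablation, interferon, high-dose interleukin-2, other anti-neoplastic medications" and "Secondary malignancy locations (6 months prior". No reason is given for that length.

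The required observation time is longer. Section 6.1 states "Study will require a minimum of 12 months of enrollment prior to the index date", and Section 6.2.1 repeats it as a criterion: "Continuous enrollment from 12 months prior to the index date".

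Eligibility also looks back further. Section 6.2.1 requires "2 or more code for secondary malignancy codes indicating possible diagnoses for metastatic disease at least 30 days apart, in the 1 year prior", with the window running to 30 days after index.

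Table 6 (Section 6.3.2) defines the history of surgery, radiation and systemic therapy, and the location of metastasis, without any look-back. Its surgical entry reads "History of nephron sparing or radical nephrectomy. ICD-10-CM Z90.5/ICD-9-CM V45.73 Acquired absence of kidney". The Optum Clinformatics description in Section 6.4 refers to an analysis window reaching 24 months before index.

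**The concern.** The codes that make a patient eligible as metastatic are also the codes that describe where the metastases are, but the two uses have different windows. The site table can therefore omit the evidence that brought a patient into the study.

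Prior surgery, radiation and cytokine therapy are facts about the past that do not lapse after 6 months. Searching a shorter period than every patient is required to have can only lower the recorded frequency.

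Describing the first-line cohorts is Objective 2, one of the primary objectives, and Section 6.7 plans standardized differences for each variable. If cohorts differ in how long before index these treatments took place, a short window shows part of that difference in timing as a difference in whether the treatment was ever given.

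**Working it through.** The plan gives no figure for capture of history, so there is none to reproduce. Index is taken as the start of aRCC treatment, as in Sections 6.1 and 6.2.1. Table 6 instead labels the index date as the first RCC diagnosis, so the anchor also needs stating.

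**Inputs**
- Required enrollment before index: 12 months (Sections 6.1, 6.2.1).
- Look-back for prior treatment and sites: 6 months (Section 6.1).
- Window for qualifying metastasis codes: 1 year before to 30 days after index, two codes at least 30 days apart (Section 6.2.1).
- Timing of events and frequency of coding: not in the documents; assumed below.

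**1. Overlap of the windows**
- Share of required enrollment not searched: 1 − 6/12 = 50%.
- Qualifying window: 365 + 30 = 395 days. Taking 6 months as 183 days, 395 − 183 = 212 days lie outside the site window, and 212/395 = 54%.
- Of those 212 days, 365 − 183 = 182 are before index and 30 are after it. A 12-month look-back closes the 182.

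**2. Can an eligible patient have no site?**
- With 6 months, yes. Codes in months -11 and -8, and none later, satisfy Section 6.2.1 and leave the site table empty.
- With 12 months including the index date, no. Two codes both dated on days 1 to 30 after index are at most 29 days apart and do not qualify. At least one qualifying code must therefore fall on or before index, within the year. The Other category in Table 6 takes any qualifying code outside the named sites.

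**3. One-time events, under assumed timing**

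Let F(t) be the probability that the event falls within t months before index. The share of 12-month events that a 6-month window misses is 1 − F(6)/F(12). For an exponential gap with mean m months, F(t) = 1 − exp(−t/m), and the share becomes exp(−6/m) / (1 + exp(−6/m)).
- m = 3: 0.135/1.135 = 12%
- m = 6: 0.368/1.368 = 27%
- m = 12: 0.607/1.607 = 38%
- Uniform over 12 months: 1 − 6/12 = 50%

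These are illustrations, not bounds. Events concentrated in months -12 to -7 would give more than 50%.

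**4. A given metastatic site that is coded repeatedly**

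With an assumed, independent monthly chance p of a claim for the site, the probability of no claim in k months is (1 − p)^k. This is not conditioned on eligibility.
- p = 0.50: 1.6% missed in 6 months, 0.0% in 12
- p = 0.20: 26% in 6, 7% in 12
- p = 0.10: 53% in 6, 28% in 12
- p = 0.05: 74% in 6, 54% in 12

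For sites coded at most visits the choice hardly matters; for sparsely coded sites it does.

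**The case against.** A single 6-month baseline for characteristics, costs and utilization is a coherent design, and the study is descriptive, with no adjustment model committed to. Table 6 gives no window and Section 6.4 mentions 24 months, so the text may be an unreconciled specification more than a deliberate choice. That stands in part: the passages do need reconciling. But Section 6.1 states 6 months explicitly for both items, and a programmer following it would apply it.

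Four stronger readings are tempting and are not supported.
- A reader might infer that half of the history is lost. The 50% describes calendar time; as a share of events it needs uniform timing. The other 6 months are not idle either: they serve the eligibility codes and support the check for no earlier aRCC treatment.
- A reader might infer that any nephrectomy in month -8 is scored as absent. The Z90.5/V45.73 status code can appear on a later claim and recover a radical nephrectomy. Nephron-sparing surgery leaves no absent kidney to code.
- A reader might infer that the loss is greatest for surgery because it comes earliest. The documents give no timing of surgery relative to systemic therapy.
- A reader might infer that 12 months removes the confusion of timing with occurrence. It only moves the cut-off further back.

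**Conclusion.** The concern holds as a minor point about cohort description. The 6-month window is shorter than both the enrollment every patient must have and the period used to establish metastatic disease, and no reason is given. It allows an eligible metastatic patient with no recorded site, and it can score one-time treatments in months -12 to -7 as absent.

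The direction is certain, because a 6-month search cannot find more than a 12-month search of the same records. The size is not known. The 12% to 50% for one-time events and the under 2% to 26% for sites with a 50% to 20% monthly chance of a claim rest entirely on assumed timing and coding frequency; sites coded less often would lose more. Eligibility and outcome definitions are unaffected.

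**What to change.** - Use the full 12 months before index, including the index date, for surgical, radiation and systemic-treatment history and for metastatic sites. Keep 6 months for baseline costs and utilization.
- State each window in Table 6, anchored to the start of aRCC treatment, and reconcile it with the 24 months in Section 6.4. Only 12 months are guaranteed, so a longer search would observe some patients for longer than others.
- Report the number of eligible patients with no recorded site, which should be zero under the 12-month rule. Running the 6-month version once alongside would show the actual size of the loss in each database.

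The cost is one window parameter, changed before programming. No extra enrollment is needed and no patient is lost. The drawbacks are that history and cost windows will differ, which table footnotes should say, and that history older than 12 months remains truncated.

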- **% continuing** – those with no gap in therapy greater than 30 days and who do not begin a new treatment during the study period.
- **% discontinuing** – those with gap in therapy greater than 30 days and who do not begin a new treatment.
- **% with treatment interruption** - those with gap in therapy greater than 30 days but who eventually continue the original treatment (have an additional administration or refill) and do not switch or augment therapy during the study period.
- **% switching** – those with gap in therapy greater than 30 days and who begin a new treatment.
- **% augmenting** – those who begin a new treatment but continue using the original treatment (have an additional administration or refill) and do not have a gap in therapy greater than 30 days of their original treatment.
- **Overall and aRCC Follow-Up Costs:** Total and RCC-specific pharmacy, medical costs from aRCC therapy index through follow-up period (costs summarized as: mean, median costs per patient and costs per patient per month).

PFIZER CONFIDENTIAL

- **Overall and aRCC Follow-Up Utilization:** Total and RCC-specific inpatient, ER, outpatient visits from aRCC therapy index through follow-up period (utilization will be summarized as: mean, median utilization per patient and utilization per patient per month).
- **Overall landmark survival:** Using Optum claims and PanTher data, landmark survival will be described and compared over follow-up time periods (3, 6, 12 months).
- **Mean/Median Survival:** Using Optum claims and PanTher data median survival time will be described and compared over follow-up time periods determined after feasibility assessments of cohorts of interest.

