6.3. Variables

6.3.1. Treatment Pattern Variables

Table 5. Treatment Pattern Variables

Variable	Operational definition
Initial (1L)Treatment Regimen	The first treatment regimen prescribed following a primary and secondary diagnosis of advanced/metastatic disease.
Monotherapy vs Combo therapy	Categorical: Yes/No Combo therapy is defined by a second medication filled on or within 30 days of the original medication and the original medication is filled subsequently. CCI [REDACTED]
Time to FL treatment received	Continuous: days Length of time (days) from the first mRCC diagnosis (first ever secondary malignancy code associated with RCC) to first line therapy prescription.
Treatment discontinuation date (by LoT) – to be used for time to treatment failure (TTF) and time to next line of therapy	Date Treatment discontinuation indicating the end of LOT will be identified as the earliest of: 
For oral therapy: to the run-out date of the last prescription (ie, date of last prescription plus days supply) in the same treatment line.For non-oral therapy: 30 days after the last observed prescription/administration prior to at least a 30 day gap in therapy of all agents included in the first line of therapy.1 day before a new prescription/administration date, whichever occurred earlier.For multiple drug regimens: the above would be triggered by the last prescription/administration in the regimen.Death.End of enrollment.
Days of continuous treatment (by LoT)	Continuous: days The duration of each LOT will be measured from the first prescription or administration of line of therapy medication(s) to the end of the line of therapy, allowing for 30 day allowable gaps in therapy.
Treatment Continuation	Categorical (Y/N) There is no >30 day gap (ie, persistent treatment) for the index medication during follow-up period.

PFIZER CONFIDENTIAL

[REDACTED]

Variable	Operational definition
Treatment Interruption	Categorical (Y/N) At least one instance of >30 day gap (ie, non-persistent treatment) for the index medication during follow-up period or LOT followed by resuming therapy (not mutually exclusive with switch, augment, discontinuation, but a sub-group within LOT).
Interrupted treatment duration	Continuous: days Time from index medication to treatment discontinuation for those within treatment interruptions (>30 day gaps). Represents the time between index and end of last treatment, including any treatment gaps.

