Regimen change (switching)	Categorical: Yes/No At least one non-index advanced/metastatic RCC medication during or after the period of the last persistent index medication prescription's days supply plus the 30 day gap (and before re-initiation of index medication or follow-up, if after).
Regimen change (augmentation)	Categorical: Yes/No Addition of treatment to initial therapy prescribed, ie, initiation of a new therapy different from the initial therapy while continuation of the initial therapy.
Line of therapy definitions	Categorical: 1L vs. 2L vs. >=3L.
Treatment sequence	Categorical: Based on observed treatment sequences. Treatment Sequence – Sequence of successive therapies for mRCC from 1L to 2L to 3L (stop after 3L).
Patient's status at end of follow-up	Categorical: end of enrollment, end of data availability, death. Patient is in one of the following mutually exclusive categories at the end of follow-up.

PFIZER CONFIDENTIAL

[figure not shown]

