6.3.3. Outcomes Variables

Table 7. Outcomes Variables

Variable	Operational definition
Days to Treatment Failure (TTF)	Time to treatment failure (TTF) is defined as the time from therapy start to treatment discontinuation for any reason, including switched, augmented therapy, end of enrollment, death.
Discontinuation	% discontinuing – those with gap in therapy greater than 30 days and who do not begin a new treatment.
Switching	% switching – those with gap in therapy greater than 30 days and who begin a new treatment.
Augmentation	% augmenting – those who begin a new treatment but continue using the original treatment (have an additional administration or refill) and do not have a gap in therapy greater than 30 days of their original treatment.
% Survived 3,6, 12 months	Mean/Median Survival Time (Days): Survival time will be described over 3,6, 12 months given follow-up time available in the data. Overall survival is defined as the length of time from index date of RCC diagnosis to patient death (or index date associated with FL Tx?) or end of available data for with no death indication. Overall landmark survival: described and compared over follow-up time periods (3,6, 12 months). Percentage of patients alive at 3,6, 12 months.
Overall Survival Time	Continuous: days Overall survival is defined as the length of time from index date of RCC diagnosis to patient death (or index date associated with FL Tx?)

PFIZER CONFIDENTIAL

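### A patient who dies on first-line therapy without a prior gap or new drug is counted as continuing, while TTF ends treatment at that same death

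*Combined protocol and SAP*

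**What the plan says.** Among the Analysis 3 outcomes, Section 6.1 defines % continuing as "those with no gap in therapy greater than 30 days and who do not begin a new treatment during the study period". Table 5 (Section 6.3.1) gives a parallel yes/no variable, Treatment Continuation: "There is no >30 day gap (ie, persistent treatment) for the index medication during follow-up period". Neither asks whether the patient is alive at the end of the window.

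Outcome follow-up in Section 6.1 runs to "the end of specified follow up period of 6 months, end of enrollment, or death".

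The percentage discontinuing covers "those with gap in therapy greater than 30 days and who do not begin a new treatment". Interruption and switching also need a gap of more than 30 days, and augmentation needs a new drug.

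Table 7 (Section 6.3.3) defines TTF as time to "treatment discontinuation for any reason, including switched, augmented therapy, end of enrollment, death", and Section 6.1 agrees. For the date that feeds TTF, Table 5 says "Treatment discontinuation indicating the end of LOT will be identified as the earliest of" a list of dates that includes death and end of enrollment. Table 5 also has a status at the end of follow-up, "Categorical: end of enrollment, end of data availability, death", which is not linked to the continuing percentage.

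**The concern.** The continuing rule is written entirely in terms of things that must be observed to happen: a gap or a new drug. Death stops observation, so a patient who dies on therapy can no longer show either. By default that patient stays in the continuing group, while the time-to-event output ends treatment on the same day.

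Persistence and discontinuation are central to the study's unmet-needs aim (Section 4), and Section 6.7 plans standardized differences for each variable. Where deaths are kept in the denominator, a regimen with more early deaths on therapy would look more persistent than it is. A reader comparing the status table with the Kaplan-Meier curve for duration of therapy could not tell why they disagree.

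**Working it through.** The plan states no figure for this quantity, so there is none to reproduce. The check is a classification exercise, an accounting identity and an illustration.

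**1. Classify one patient.** Take a patient who starts first-line therapy, fills or receives it without a gap of more than 30 days, takes no new drug, and dies before the window closes.

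| Output | Rule | Result |
|---|---|---|
| % continuing (6.1) | no gap, no new drug | yes |
| Treatment Continuation (Table 5) | no gap during follow-up | yes |
| % discontinuing, interrupted, switching (6.1) | each needs a gap | no |
| % augmenting (6.1) | needs a new drug | no |
| TTF (6.1, Table 7) | death is listed | treatment ended |
| Discontinuation date (Table 5) | death is listed | treatment ended |

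The only treatment status open to this patient is continuing. The end-of-follow-up status records the death but does not move the patient.

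**2. Identity.** For any analysis set that keeps these patients:

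% continuing as written = share alive and on therapy at the end of the window + share who died on therapy with no prior gap or new drug.

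The excess is the second term.

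**3. Illustration with assumed rates.** Let s be the monthly hazard of stopping or switching, d the monthly hazard of death on therapy, and T the window in months. Both hazards are assumptions, taken as constant, and a gap is treated as seen at once.

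- Alive and on therapy = exp(−(s+d)T)
- Excess = d/(s+d) × [1 − exp(−(s+d)T)]
- As written = the sum of the two

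With T = 6, s = 0.05 and d = 0.01: exp(−0.36) = 0.698. The excess is (0.01/0.06) × 0.302 = 0.050, and the sum is 0.748.

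| T | s | d | As written (%) | Alive and on therapy (%) | Excess (points) |
|---|---|---|---|---|---|
| 3 | 0.05 | 0.03 | 86.7 | 78.7 | 8.0 |
| 6 | 0.05 | 0 | 74.1 | 74.1 | 0.0 |
| 6 | 0.05 | 0.01 | 74.8 | 69.8 | 5.0 |
| 6 | 0.05 | 0.03 | 76.2 | 61.9 | 14.3 |
| 6 | 0.10 | 0.01 | 56.1 | 51.7 | 4.4 |
| 6 | 0.10 | 0.03 | 58.3 | 45.8 | 12.5 |
| 12 | 0.05 | 0.01 | 57.2 | 48.7 | 8.6 |
| 12 | 0.05 | 0.03 | 61.4 | 38.3 | 23.1 |

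(The excess is computed before rounding.) The direction matters more than the size. At 6 months with s = 0.05, raising d from 0 to 0.03 lifts the figure as written from 74.1% to 76.2%, while the share alive and on therapy falls from 74.1% to 61.9%.

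**4. Are such patients in the denominator?** Section 6.2.1 selects patients whether or not they survive, outcome follow-up may end at death, and survival at 3, 6 and 12 months is a planned outcome. These point to keeping deaths. Against that, Section 6.2.1 requires enrollment from index to the end of the data, Section 6.1 requires at least 6 months of post-index enrollment for duration of therapy, and Section 6.7 matches the windows to the 3-, 6- and 12-month cohorts. If death counts as loss of enrollment, then d = 0 within each window and the excess is zero. The documents do not say which applies.

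**The case against.** The strongest reply is that the enrollment rules already remove the affected patients. Outcomes are assessed in cohorts defined by 3, 6 and 12 months of continuous enrollment, and each window equals the enrollment required. Someone who disenrolls inside the window is not in that cohort. If death ends enrollment, neither is someone who dies. Section 6.1 does present first-line cohorts for all patients whatever their follow-up, but it does not say that % continuing is computed on that set.

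This stands for disenrollment in the matched cohorts. A reader might infer that patients who leave their plan on therapy are also wrongly counted as continuing. Section 6.2.1 would make them ineligible, and their later treatment is unknown rather than failed. A reader might also infer that, in databases without death data, deaths show up as end of enrollment and then count as continuing. No section says so, and the same eligibility rule would remove them.

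For deaths the reply does not settle the matter. If death were loss of enrollment and the rule in Section 6.2.1 were applied strictly, nobody who died before the end of the data could be in the study, and the planned survival analysis would have no events. Selecting patients irrespective of survival and ending follow-up at death would then serve no purpose.

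It is also fair to say that a gap-based status and a composite time measure may differ by design, that the study is descriptive, and that death is already recorded in Table 5. These points limit the seriousness. They do not tell the programmer or the reader where a death on therapy belongs in the status table.

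**Conclusion.** The point holds in conditional form. The written rules place a death on therapy, with no prior gap or new drug, in the continuing group and nowhere else, while TTF and the Table 5 discontinuation date end treatment there. No section reconciles the two.

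It would go too far to say that % continuing is overstated without qualification, or to attach a figure such as 5 to 15 points. The documents give no death rate, and the excess is zero under one reading of the enrollment rules. The ranges under the assumed hazards (0 to 14.3 points at 6 months, 0 to 23.1 at 12 months) show scale only and are not estimates for this population. The conclusion for any given table rests on one unstated fact: whether patients who die before the window closes stay in the denominator. The signs in the protocol favor keeping them. The change is worth making because, where they are kept, the error favors regimens with more early deaths.

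**What to change.** Amend Section 6.1 and Table 5, and align Table 7, as follows:

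- Define continuing as on the index regimen, with no gap of more than 30 days and no new agent, through the end of the window.
- Report died on therapy as its own status in the databases that hold death data.
- Report enrollment ended on therapy as a separate status, unknown (censored), neither continuing nor failure.
- State whether patients who die before the window closes stay in the denominator of the 3-, 6- and 12-month cohorts, and whether death counts as loss of enrollment.
- Make TTF, the discontinuation date and the end-of-follow-up status treat these patients in the same way.

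The cost is wording and two more rows in one table. % continuing will be slightly lower where deaths are retained. Died on therapy can be separated only where deaths are recorded: Section 5 limits survival analysis to Optum Clininformatics, while Section 6.1 also names PanTher. The other databases need a footnote saying that death cannot be distinguished.
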